**Table 2: Patient characteristics collected**

	Data	Origin	Details
Patient information			
A *	Name	Medical record	Name
B*	Date of birth* (if applicable)	Medical record	Date of birth: ...../...../.....
C*	Mailing Address* (if applicable)	Medical record	Address:
D*	Phone number* (if applicable)	Medical record and patient interview	Phone number :  Cell phone number :
E**	E-mail address	Medical record and patient interview	Address:
1	Participant number		
2	Age	Medical record	Age:
3	Type	Medical record	 Male  Woman
4	Civil status	Medical record	 Single  Married  Divorced  Widow(er)
5	Origin	Medical record	 Switzerland  Central Europe  Southern Europe  Southeast Europe  Northern Europe  Western Europe  Eastern Europe  Africa  Asia  Other
6	Ethnicity	Patient interview	 Caucasian  African  Asian  African American

			 Other
7	Level of education	Patient interview	 Primary level (compulsory school)  Vocational secondary level (CFC, ECG)  Secondary II general level (Federal Maturité)  Higher vocational training I (Federal diploma, ES)  Higher Vocational Education II (Federal Master's Degree)  Universities I (Bachelor) (UNI/HES/EPF)  Universities II (Master) (UNI/HES/EPF)  Universities III (PhD) (UNI/HES/EPF)  Other
8	Employment	Patient interview	 Full-time professional activity  Part-time professional activity  Unemployed  Retired  Unemployed (house parent)  Unemployed (DI, social assistance)  Other
9	Annual income	Patient interview	 < 20'000 CHF  20'000-50'000 CHF  50'000-100'000 CHF  100'000-200'000 CHF  > 200'000 CHF  I do not wish to answer
10	Mother tongue	Medical record and patient interview	 French  Swiss-German  Italian  Romanche  German  English  Spanish  Portuguese  Other
11	Level of understanding of the French language	Patient interview	 Native  Excellent  Good  Average  Low
12	Level of expression in French language	Patient interview	 Native  Excellent  Good  Average  Low
13	Assay-Curological Profile	Medical record and patient interview	 Basic insurance  Supplementary insurance  Private Insurance
14	Life context	Medical record and patient interview	 Lives alone  Lives with partner  Lives with children  Other
15	Owner of a smartphone or a tablet	Patient interview	 Yes  No
16	Computer owner	Patient interview	 Yes

			 No
17	Internet connection at home	Patient interview	 Yes  No
18	Ability to use a smartphone, tablet, computer	Patient interview	 Basic (phone, SMS)  Means (e-mail, internet search Some basic applications)  Advanced (daily use, application installation)
19	Preference of the means of communication for contact at home	Patient interview	 Phone  E-mail  Mail  Video-conference
20	Frequency of e-mail use	Patient interview	 Every day  Several times a week  1 time per week  A few times a month  A few times a year  Never, because I don't have an e-mail address
Medical data			
21	Active co-morbidities	Medical record	Names to be specified:
22	Cardiovascular history	Medical record	 Acute coronary syndrome  Angina  Atrial fibrillation  Rhythm disorders  Valvulopathy  Cardiac decompensation  Pericarditis  Myocarditis  Endocarditis  Dilated/hypertrophic/restrictive cardiomyopathy  Sarcoidosis  Congenital heart disease  Cardiogenic shock  Cardiorespiratory arrest  Cardio-renal syndrome  Coronary artery disease  Arterial insufficiency of the lower limbs  Thrombo-embolic disease  Cerebrovascular accident  Pulmonary embolism  Other
23	Cardiovascular risk factors	Medical record	 Hypertension  Diabetes  Dyslipidemia  Obesity  Tobacco  Alcohol  Drug  Family history IM

24	Psychic disorders	Medical record/patient interview/investigating physician	 Absent  Present Type if present :  Depression  Anxiety  Bipolar Disorders  Other
25	Cognitive disorders	Medical Record/Patient Testing	 Absent  Present
26	MMS Score	Medical Record/Patient Testing	Number and date: ..... (...../...../.....)
27	Score Clock Test	Medical Record/Patient Testing	Number and date: ..... (...../...../.....)
Heart Failure Data			
28	NYHA classification of IC (at admission)	Medical record	 Class I  Class II  Class III  Class IV
29	FEVG (before admission if known)	Medical record	Number (%) and date: .....% (...../...../.....)  Category:  HFrEF <40%.  HFmrEF 41-49
30	LVEF (on admission to hospital)	Medical record	Number (%) and date: .....% (...../...../.....)  Category:  HFrEF <40%.  HFmrEF 41-49
31	Cause of acute heart failure	Medical records/Patient's physicians	 High blood pressure  Ischemic heart disease  Rhythmic heart disease  Valvular heart disease  Cardiomyopathy (hypertrophic, dilatative, restrictive, myocarditis etc.)  Infiltrative heart disease (sarcoidosis, amyloidosis, connectivitis, hemochromatosis)

			 Structural heart disease  Medicated/Toxic  Endocrinopathy  Systemic infection  State of shock  Poor adherence to therapy  Hypervolemia  Renal insufficiency  Other
32	New diagnosis of heart failure	Medical records/Patient's physicians	 Yes  No
33	History of hospitalization for heart failure	Medical records/Patient's physicians	 Yes  No
34	Hospitalization for cardiac decompensation in the last 12 months	Medical record and patient interview	 Yes  No
35	Cardiovascular medical device	Medical record	 Pacemakers  Cardiac Resynchronization Therapy (CRT)  Automatic Implantable Defibrillators (AIDs)/  Left ventricular assist (LVA)
Laboratory data			
36	NT-proBNP (admission)	Medical record	Number (ng/L) and date: ..... ng/L (...../...../.....)
37	Creatinemia (admission)	Medical record	Number ( $\mu\text{mol/L}$ ) and date: ..... $\mu\text{mol/L}$ (...../...../.....)
38	eGFR (admission)	Medical record	Number ( $\text{mL/min/1.73 m}^2$ ) and date: ..... $\text{mL/min/1.73 m}^2$ (...../...../.....)
Vital parameters data			
39	Heart rate (admission)	Medical record	Number (bpm) and date: .....bpm (...../...../.....)
40	Systolic blood pressure (admission)	Medical record	Number (mmHg) and date: .....mmHg (...../...../.....)

41	Diastolic blood pressure (admission)	Medical record	Number (mmHg) and date: .....mmHg (...../...../.....)
42	Weight (admitted)	Medical record	Number (kg) and date : .....kg (...../...../.....)
43	Weight (exit)	Medical record	Number (kg) and date : .....kg (...../...../.....)
44	Body mass index (Kg/m  )	Medical record	 <18  18-24.9  25-29.9  30-34.9  35-39.9  ≥40 
Drug Data			
45	Medication at home before admission	Medical record	Date: (...../...../.....)  Specialty / INN / Dosage / Dosage e.g. Forxiga, dapagliflozin, 10mg, i.d
46	Number of medications before hospitalization	Medical record/patient interview/	 0  1-2  3-4  >4
47	Number of heart failure medications prior to hospitalization	Medical record/patient interview/	 0  1  2  3  4  5  >5

48	Heart failure medication list (home)	Medical record	 Diuretic  Beta-blocker  IECA/ARA  ARNI  Aldosterone antagonist (ARM)  SGLT2 inhibitor  Ivabradine  Digoxin  Vericiguat
49	Heart failure medication list (hospitalization)	Medical record	 Diuretic  Beta-blocker  IECA/ARA  ARNI  Aldosterone antagonist (ARM)  SGLT2 inhibitor  Ivabradine  Digoxin  Vericiguat
50	Heart failure medication list (hospital discharge)	Medical record	 Diuretic  Beta-blocker  IECA/ARA  ARNI  Aldosterone antagonist (ARM)  SGLT2 inhibitor  Ivabradine  Digoxin  Vericiguat
51	Medication management in the home	Patient interview	 Autonomous  Nursing care  Pharmacy  Caregivers
52	Medication management tool	Patient interview	 Paper Medication Plan  Electronic Medication Plan  Weekly/Plus  Daily unit dose sachet  Unit discount by the pharmacy  Other
53	Frequency of visits to your regular pharmacy	Patient interview	 Several times a week  1 time per week  2-3 times a month  1 time per month  1 time every 2-3 months  2 times a year  1 time per year  Never
54	Quality of the relationship with your city pharmacist	Patient interview	 No particular relationship  Wrong  Neither good nor bad  Good  Very good
Pre-test data			
55	Knowledge Questionnaire	Patient interview	Answer for each question (detailed in the documents specific to the questionnaires)
56	Score	Calculation	Value:
57	Belief questionnaires	Patient interview	Answer for each question (detailed in the documents specific to the questionnaires)

58	Need score	Calculation	Value:
59	Concern score	Calculation	Value:
60	Differential score	Calculation	Value:
61	Membership questionnaire	Patient interview	Answer for each question (detailed in the documents specific to the questionnaires)
62	Membership score	Calculation	Value:
Post-interview FTE data (for intervention group only)			
63	Knowledge Questionnaire	Patient interview	Answer for each question (detailed in the documents specific to the questionnaires)
64	Score	Calculation	Value:
65	Satisfaction questionnaire	Patient interview	Answer for each question (detailed in the documents specific to the questionnaires)
Output data (3-7 days) (for intervention group only)			
66	Length of stay in acute care hospitals	Medical record	Number of days :  Category:  0-3 days,  3-7 days  7-10 days  10-14 days  14 -30 days  > 30 days
67	Place of transfer at the end of the hospitalization	Medical record	 Home  Rehabilitation Service  Other acute care unit  Other acute care service  Other hospital
68	Follow-up by a cardiologist	Patient interview	 Yes  No
69	Date of cardiologist's visit	Patient interview	date:  (...../...../.....)
70	Weight at home	Patient interview	Number (kg) and date :  .....kg  (...../...../.....)
71	Increase in weight	Patient interview	 Yes  No  If yes, number of kilograms :
72	Symptoms of heart failure	Patient interview	 Water accumulation in the ankles, legs, abdomen or lungs  Shortness of breath when making an effort  Difficulty breathing, sometimes with a dry cough

			 The sensation of suffocation in the supine position  Rapid weight gain (>2kg in 3 days)  Fatigue  Dizziness  Palpitations  Chest pain
73	Pharmacy visited	Patient interview	Name:  Date: ...../...../.....  Number of days after hospitalization: .....
74	Obtaining medication	Patient interview	 Yes  No If so, what type?  Delayed delivery time of 1-2 days because your pharmacy had to order certain medications.  Delayed delivery time of more than 1 week because your pharmacy had to order certain medications.  Delayed time to obtain and date of obtaining still undetermined  Inability to get to the pharmacy on your own  You forgot to pick them up  Other (please specify): ..... ..... .....
75	Heart failure medication list	Patient interview	Date: (...../...../.....)  Specialty / INN / Dosage / Dosage e.g. Forxiga, dapagliflozin, 10mg, i.d
76	Adverse drug reactions	Patient interview	 Extreme fatigue  Dizziness when you stand up  Vision problems  Headaches  A frequent need to urinate  Low blood pressure (<110mmHg)  A low heart rate (<60 bpm)  Rapid weight gain (>2kg in 3 days)

			 Worsening of shortness of breath or edema  Dry cough  Dry mouth and intense thirst  Dry skin
77	Physical and moral feelings of the patient on returning home	Patient interview	Free response
78	Experience and feeling of going home	Patient interview	Free response
Post-test data at 1 month			
79	Knowledge Questionnaire	Patient interview	Answer for each question (detailed in the documents specific to the questionnaires)
80	Score	Calculation	Value:
81	Belief questionnaires	Patient interview	Answer for each question (detailed in the documents specific to the questionnaires)
82	Score need	Calculation	Value:
83	Concern score	Calculation	Value:
84	Differential score	Calculation	Value:
85	Membership questionnaire	Patient interview	Answer for each question (detailed in the documents specific to the questionnaires)
86	Score	Calculation	Value:
87	Satisfaction questionnaire	Patient interview	Answer for each question (detailed in the documents specific to the questionnaires)
88	CardioMeds Usability Questionnaire	Patient interview	Answer for each question (detailed in the documents specific to the questionnaires)
89	CardioMeds Self-Care Questionnaire	Patient interview	Answer for each question (detailed in the documents specific to the questionnaires)
90	Heart failure medication list	Patient interview	Date: (...../...../.....)  Specialty / INN / Dosage / Dosage e.g. Forxiga, dapagliflozin, 10mg, i.d
91	Re-hospitalization 1 month after hospitalization	Patient interview	 Yes  No
92	Emergency visits (Hospital/Ambulatory ) 1 month after hospitalization	Patient interview	 Yes  No
93	Deaths 1 month after hospitalization	Medical records, relatives, attending physician	 Yes  No

\*This participant identification data will not appear in the participant's Case Report Form (CRF). It will be collected by the investigator and stored separately from the CRF in a secure electronic file accessible only by the investigator and the CRA.

\*\* The e-mail address will be visible in the eCRF but only consultable by the investigator and the clinical research associate. It must appear in the CDMS (RedCap™) to allow the setting of the sending of the questionnaires at 1 month for the participants having wished to receive them by e-mail. As soon as all the participant's data have been collected and the study is closed, the e-mail addresses will be deleted from the CDMS.

For any data that is not complete during hospitalization, it will be obtained by phone call upon the participant's return home.

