## Conduct of the study

## Data collected

Baseline patient information, medical data, heart failure data, laboratory data, vital parameter data, medication data will be collected for each patient included in the study once the consent form is completed. Other study data will be collected for pre-testing after randomization.

The data collected for the intervention group will be collected after the teaching interview, during the telephone call upon discharge and for the post-test at 1 month after discharge. Data for the control group will be collected for the post-test at 1 month after discharge.

All these data are presented in Table 2.

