## **5 STATISTICS AND METHODOLOGY**

This chapter of the protocol describes the research hypotheses, statistical analysis plan, sample size, and treatment of missing data.

It was submitted to [name], head of the methodological support unit of the HUG clinical research center, who assisted us in the construction of these elements and their validation.

The final analysis will be based on the intention-to-treat principle, i.e. including all patients who were randomized in the study.

For the basic data, continuous variables will be described as means and standard deviation, median and inter-quartile range.

The discrete or categorical variables will be described by their numbers and relative proportion, or even the mean and standard deviation, depending on the variables

Some continuous data such as age, left ventricular ejection fraction (LVEF), laboratory data, length of hospital stay, number of pre- and post-hospitalization medications will be reclassified into categories and presented as numbers and relative proportion of each category. Differences in outcomes between the intervention and control groups will be analyzed using the t-test for continuous variables and a Chi-Square test for categorical variables.

The main analysis assessing knowledge status will compare the knowledge score (dependent variable) between the two randomization groups (main independent variable) after adjusting for knowledge status at baseline using a linear regression model or ANCOVA.

For continuous secondary outcomes (medication beliefs and medication adherence), a Student's t test will also be used to compare mean values between the two groups. For binary outcomes (re-hospitalization or new emergency department visit within 1 month), a chi-2 test (or Fisher exact test if the smallest expected number of patients is <5) will be used.

For the satisfaction outcome, which is an ordinal qualitative variable, a Chi-2 test (or Fisher's exact test if the smallest expected number of participants is <5) will be used.

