## 6.5 (Premature) study termination

The sponsor and the principal investigator may terminate the study prematurely under certain circumstances, such as

- Ethical issues,
- Insufficient recruitment of participants,
- When participant safety is in doubt or at risk (e.g., when the benefit-risk assessment is no longer positive),
- Changes in accepted clinical practice that make it unwise to continue the study, or
- Early evidence of harm or benefit from the experimental intervention.

In the event of the regular termination of the study, the ethics committee is informed via BASEC within 90 days (ClinO, art. 38).

In the event of premature termination or interruption of the study, the ethics committee is informed via BASEC within 15 days (ClinO, art. 38).

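### Table 2 collects length of stay, discharge destination, symptoms and drug reactions in the intervention arm only: a planned descriptive variable lacks control values, and non-serious events are ascertained unequally

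*Combined protocol and SAP*

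**What the plan says.** Table 2 in section 4.3 groups its 93 numbered items into blocks. The block headed "Output data (3-7 days) (for intervention group only") runs from item 66 to item 78. It contains:

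- item 66, "Length of stay in acute care hospitals", and item 67, "Place of transfer at the end of the hospitalization", both with the medical record as source;
- item 72, "Symptoms of heart failure", and item 76, "Adverse drug reactions", both tick lists completed by patient interview.

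The text under Data collected in section 4.3 agrees with the table. After baseline and pre-test, it says "Data for the control group will be collected for the post-test at 1 month after discharge".

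Section 5 plans that "length of hospital stay, number of pre- and post-hospitalization medications will be reclassified into categories and presented" as numbers and proportions. Neither it nor the matching paragraph of the synopsis limits this to one arm, and in both the next sentence describes between-group tests.

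Section 6.2 defines an adverse event broadly enough to include any unfavourable symptom, related to the trial procedure or not, and asks for all adverse events to be documented. Section 8.2 makes adverse events part of every participant's case report form. Among the grounds for early termination, section 6.5 lists "When participant safety is in doubt or at risk (e.g., when the benefit-risk assessment is no longer positive") and early evidence of harm or benefit.

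**The concern.** There are two separate problems.

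First, the analysis text and the collection table disagree. Length of stay is to be described for the trial population, but the table provides it for one arm. Discharge destination has the same gap, although neither item needs contact with the patient.

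Second, the two arms are not asked about non-serious events in the same way. An intervention patient is taken through two prompted lists within a week of discharge. A control patient is not, and the 1-month block (items 79-93) has no symptom or reaction list for either arm. If ticked boxes are entered as adverse events, the intervention arm can show more events because it was asked more. A real excess could be dismissed as an artefact, or an artefact taken for a signal. Either would be a poor basis for a review under section 6.5.

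**Working it through.** The plan gives no figure to reproduce on this point. The check compares passages, with three short calculations.

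**1. Extent of the one-arm block.** Items 66 to 78 are 78 − 66 + 1 = 13 of 93 numbered items. Two (66, 67) come from the record. The other 11 (68-78) come from the interview, and several, such as the pharmacy visited or feelings on returning home, belong naturally to the call. Item 72 lists 9 symptoms and item 76 lists 12 reactions, so there are 9 + 12 = 21 prompts. Rapid weight gain is on both lists.

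**2. Length of stay against its source.** The variables that section 5 names for categorisation can be traced in Table 2:

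| Variable | Table 2 source | Arms |
|---|---|---|
| Age | item 2 | both |
| LVEF | items 29-30 | both |
| Laboratory data | items 36-38 | both |
| Medication before admission | items 46-47 | both |
| Heart failure medication at discharge and 1 month | items 50, 90 | both |
| Length of stay | item 66 | intervention only |

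Only length of stay has its source in a one-arm block. Controls' records are opened around discharge anyway, because weight at exit (item 43) and discharge medication (item 50) are recorded for everyone. Section 8.2 also stores dates of stay.

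**3. Which harm data cover both arms.**

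| Information | Where | Arms |
|---|---|---|
| Readmission, emergency visits | section 4.3; items 91-92 | both |
| Being seen for signs of decompensation | section 4.3, 1-month call | both |
| Death at 1 month | section 3.2; item 93 | both |
| Adverse and serious adverse event recording | sections 6.2, 8.2 | no restriction |
| Prompted symptoms and reactions, days 3-7 | items 72, 76 | intervention only |

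Death and hospitalisation are serious events under section 6.2, so serious harm has a control comparator. Non-serious events have one only through unprompted reporting. Section 3.2 blurs this by also listing readmission, emergency visits and death among endpoints assessed in the intervention group. That conflicts with the between-group comparison of unplanned care and the two-group death rate in the same section, and with section 4.3.

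**4. Possible size of the ascertainment artefact.** Let *t* be the share of intervention patients who tick at least one reaction and *s* the share of controls who report one unprompted. With equal true rates and 45 per arm, the spurious excess is 45 × (*t* − *s*). The documents give neither value. Assuming *t* between 20% and 50%, 45 × 0.20 = 9 and 45 × 0.50 = 22.5 intervention patients would have a solicited event. As *s* runs from 0 up to *t*, the excess runs from that number down to nil. The direction is predictable; the size is not.

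**5. What the two-arm outcomes can detect (context).** For *n* per arm and two-sided 5%, with p̄ the mean of p₁ and p₂:

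power = Φ{[√n·|p₂ − p₁| − 1.96·√(2p̄(1 − p̄))] / √[p₁(1 − p₁) + p₂(1 − p₂)]}

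For n = 45, 7% against 14%: (6.708 × 0.07 − 1.96 × 0.4335) / 0.4307 = −0.883, and Φ(−0.883) = 0.19. The base rates below are the 30-day readmission rates quoted in section 2 (in-house, assumed for the standard population, and literature). The doubling is an assumption.

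| Rates | n = 40 | n = 45 | n = 62 |
|---|---|---|---|
| 7% to 14% | 17% | 19% | 24% |
| 15% to 30% | 36% | 40% | 52% |
| 25% to 50% | 64% | 69% | 83% |

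These comparisons are fair between arms but mostly weak.

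**The case against.** The strongest reply is that the call at days 3-7 is the third component of the intervention (section 3.4), so collecting its findings in one arm follows from the design. That stands for items 68-78. It does not explain items 66 and 67, which come from the record.

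A second reply is that sections 5 to 5.2 plan no between-arm adverse event comparison, and nothing says that ticked boxes become adverse event counts. The sentence requiring all adverse events to be documented also sits under a heading about serious events, so serious events may be what was meant. This makes the artefact conditional. It does not remove it, because section 8.2 lists adverse events as a case report form element and section 6.5 allows termination on safety grounds.

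A reader might go further and infer four things that the documents do not support:

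- *No harm can be judged against control.* Readmission, emergency visits, death and serious events cover both arms.
- *Length of stay cannot be compared.* Control values can be retrieved from the record. Length of stay is also not a named endpoint.
- *Controls will have essentially no recorded events.* Recording is not restricted by arm, and unprompted reports are possible.
- *Without discharge destination, the 1-month windows cannot be aligned.* The discharge date sets the start. Whether a rehabilitation stay postpones discharge is a separate question of definition that item 67 does not settle.

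It is also tempting to equalise the arms by adding both checklists to the 1-month contact. The primary knowledge questionnaire is completed at that contact, and it tests decompensation symptoms and adverse effects of the main drug classes (section 3.2), so the lists could cue answers. Nor would reporting become equal: intervention patients are taught adverse effects by quiz and fill in a card of those to watch for (section 3.4).

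**Conclusion.** The point holds as a conflict over length of stay and as unequal ascertainment of non-serious events. Following Table 2 leaves length of stay, a planned descriptive variable, and discharge destination without control values. It also has 21 symptom and reaction prompts put to one arm only.

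The first part rests on the text alone. The second depends on call findings entering the adverse event record, which the protocol permits but does not state. Given that, the bias is towards more events in the intervention arm; the 9 to 23 patients calculated above rest on an assumed tick rate and form an upper bound under it. Serious harm remains comparable between arms, though with limited power (19% at 45 per arm for a doubling from 7%). The primary analysis is not affected. The point should be corrected, but it does not threaten the trial's main conclusion.

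**What to change.** 1. Move items 66 and 67 out of the intervention-only block and take them from the medical record in both arms.
2. State that the findings of the day 3-7 call (items 68-78) are reported as description of the intervention arm only. Exclude events solicited at that call from any between-arm adverse event comparison and from any comparative safety review under section 6.5. Base those on outcomes collected the same way in both arms: death, readmission, emergency visits and record-based serious events. Individual reporting under section 6.2 is unchanged.
3. Reconcile section 3.2 with itself and with section 4.3, so that readmission, emergency visits and death are clearly collected in both arms.

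Asking items 72 and 76 at 1 month is optional. If it is done, they should be asked identically in both arms, only after the knowledge questionnaire has been completed, and read with caution because intervention patients were taught to recognise adverse effects.

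The cost is two record fields per control patient: 2 × 45 = 90 entries at the required size, or 2 × 62 = 124 at the expected size. No visit, call or patient contact is added.
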